### 7.5. **Concomitant Medications and Other Guidance**

All concomitant medications used during the study and within 14 days prior to Screening must be reported on the appropriate CRF.

#### 7.5.1. **Prohibited Medications/Procedures**

- Chemotherapy, radiation therapy, hormonal therapy or any investigational anti-neoplastic agent for the active treatment of cancer are prohibited. Patients may continue on adjuvant hormonal therapy for prostate or breast cancer, as long as there is no detectable disease at study entry.
- Systemic steroids, at doses greater than the equivalent of 20 mg prednisone daily, with the exception of intermittent use for the treatment of emesis, are prohibited. Steroid inhalers for medical conditions are permitted. Patients needing pulse corticosteroids for other medical conditions should be discussed with the Sponsor’s Medical Monitor.

- Nasal flu vaccine is prohibited because the nasal vaccine is a live, attenuated virus; however, flu injections, which are nonviable antigens, are permitted (see Section 7.5.2).

### 7.5.2. **Permitted or Mandated Medications**

- Anti-emetic agents for the treatment of nausea and vomiting are permitted.
  - No constraint will be placed on the use of growth factors during subsequent treatment; however, prophylactic use is discouraged and adherence to American Society of Clinical Oncology (ASCO) guidelines is recommended.

#### 7.5.2.1. ***Antimicrobial Prophylaxis***

- *Pneumocystis* prophylaxis is required in all patients receiving cerdulatinib, and study patients should be monitored closely with frequent cell counts for evidence of infection or bone marrow suppression. Bactrim™ (sulfamethoxazole/trimethoprim) 1 DS tab/day is the recommended prophylaxis regimen and will cover both *Pneumocystis jirovecii* and *Nocardia*. Other recommendations may be found in the National Comprehensive Cancer Network (NCCN) guidelines [77]. For patients unable to take Bactrim, atovaquone, or pentamidine (inhaled or IV) may be considered. Dapsone is not recommended because of the potential for drug interactions and methemoglobinemia.
- Patients should also receive prophylaxis for herpes simplex virus infection per NCCN guidelines [77].
- Immunizations or vaccinations (for such things as influenza or pneumonia) are encouraged prior to study entry. Note that nasal flu vaccines should not be administered to patients because the nasal vaccine is a live, attenuated vaccine, whereas flu shots are nonviable antigens (see Section 7.5.1).
- Prophylaxis for tumor lysis syndrome is permitted at the discretion of the treating physician, based on clinical characteristics.

### 7.5.3. **Cerdulatinib and CYP3A4**

Cerdulatinib is a substrate for CYP3A4 and may also decrease expression levels of CYP3A4 enzyme activity in patients, thus potentially augmenting the AE profile of other drugs. To avoid possible drug-drug interactions, strong inhibitors, CYP3A sensitive substrates, and inducers of CYP3A4 should be avoided in patients receiving cerdulatinib. An inhibitor of CYP3A4 would reduce the metabolism of cerdulatinib and could result in high concentrations that could cause AEs. An inducer of CYP3A4 could result in lower than desired levels of cerdulatinib and lessen the likelihood of efficacy. Additionally, cerdulatinib can cause other medications to accumulate to levels that result in toxicity due to lower levels of CYP3A4 being expressed. Because of this effect CYP3A sensitive substrates need to be considered. If the Investigator feels that use of a strong inhibitor or strong inducer of CYP3A4 is necessary, this should be discussed with the Sponsor's Medical Monitor. [Appendix 3](#) provides a list of such CYP3A4 substrates and strong

inhibitors/inducers. Physicians should monitor for potential drug-drug interactions, and a dose adjustment (lowering) for CYP3A sensitive substrates should be considered on a case-by-case basis by the treating physician.

#### **7.6. Study Committee**

Select study participants will comprise the Study Committee (e.g., the selected Principal Investigators, Portola's Medical Monitor, Clinical Study Manager, and/or Drug Safety Medical Monitor). Other Portola or outside personnel may be called or consulted as needed.

- Phase 1: Upon the completion of the initial 28-day treatment period (Cycle 1) for all patients in any cohort, the Study Committee will convene via teleconference or in person to review all available DLT, AE, and any other clinical or laboratory data for the patients in that cohort. The Study Committee will determine whether it is safe to escalate to the next dose level of cerdulatinib or whether the MTD or MAD has been reached. If it is safe to continue, the Study Committee will determine the next dose level to be studied.
- Phase 2a: The Study Committee will meet periodically to review available safety and efficacy data from the study. Following the first meeting of the Study Committee, subsequent meetings will be held periodically as needed. Members of the Portola study team, such as representatives from Biostatistics, Drug Safety, Clinical Development, and Clinical Operations may participate in the meetings as needed. Data to be evaluated may include (but are not limited to): deaths, other SAEs; AEs, including treatment-related AEs; reasons for treatment discontinuation or dose modification/ interruption, trends in laboratory evaluations, and efficacy.
- For the combination cohort with rituximab, the Study Committee will evaluate (using the assessments as outline above) the first 3 to 6 patients who have completed Cycle 1 before allowing further enrollment in the cohort. Afterwards, the cohort can be evaluated with the rest of the other cohorts as above.

## **8.0 ASSESSMENT OF EFFICACY**

### **8.1. Response Criteria**

Response in NHL patients will be evaluated using The Lugano Classification [4]; in CLL patients using the Workshop on Chronic Lymphocytic Leukemia (IWCLL) Guidelines for the Diagnosis and Treatment of Chronic Lymphocytic Leukemia [2]; in leukemic forms of PTCL (ATLL, PLL, LGL) using disease appropriate response criteria [77]; and in CTCL patients using the modified Severity Weighted Assessment Tool (mSWAT) and other measures as appropriate [5]. [Appendix 4](#) provides definitions and detailed descriptions of response criteria as well as guidance on selection of lesions for evaluation. Redacted copies of radiology reports will be sent to the Sponsor for review.

### **8.2. Exploratory Efficacy**

#### **8.2.1. Global Health Questionnaire**

Patients will be asked to complete a Global Health Questionnaire ([Appendix 8](#)) to assess whether patients feel their overall health is improving on this study. The correlation between markers of inflammation with clinical response and the Global Health Assessment will be evaluated.

## 9.0 PHARMACOLOGY ASSESSMENTS

### 9.1. Pharmacokinetic Assays

Plasma samples will be obtained at selected time points (detailed in [Appendix 1](#)) and analyzed for the concentration of cerdulatinib and possible metabolite identification. Sample assay for drug concentrations will be performed using a validated LCMS method. Details on the collection, processing, storage, and shipment of samples are contained in the Study Laboratory Manual.

#### 9.1.1. Phase 1 Pharmacokinetic Analysis

The following PK parameters of cerdulatinib will be calculated for all patients:

- Plasma half-life ( $t_{1/2}$ ), determined by linear regression of the log concentration on the terminal portion of the plasma concentration-time curve. Terminal half-life is calculated as  $\ln(2)/(-\beta)$ , where  $\beta$  is the slope of the terminal portion of the log concentration-time curve.
- Time to maximum observed plasma concentration ( $T_{max}$ ).
- Maximum observed plasma concentration ( $C_{max}$ ).
- Minimum observed plasma concentration ( $C_{min}$ ).
- Area under the plasma concentration-time curve from 0 to last measurable concentration ( $AUC_{0-last}$ ) computed using the linear trapezoidal rule.
- Total area under the plasma concentration-time curve from time 0 to infinity ( $AUC_{0-\infty}$ ), computed as:

$$AUC_{0-\infty} = AUC_{0-last} + C_{plast} / (-\beta)$$

where  $AUC_{0-last}$  is the area under the curve from time 0 to the time point of the last measurable concentration above the quantitation limit;  $C_{plast}$  is the last measurable concentration above the quantitation limit; and  $\beta$  is defined as above.

- Clearance of cerdulatinib (CL/F).
- Volume of distribution of cerdulatinib at steady state ( $V_{ss}/F$ ).
- Amount of drug excreted in urine over the sampling interval ( $A_e$ ) for those patients for whom total volume of urine was collected.
- Accumulation ratio, calculated by  $AUC_{0-12}$  at steady-state/ $AUC_{0-12}$  following the first dose for those patients for whom the 12 hour sample was collected.

### **9.1.2. Phase 2a Pharmacokinetic Analysis**

In order to further characterize the PK of cerdulatinib (specifically,  $C_{min}$ ), plasma samples during the Phase 2a portion of the study will be taken pre- and post-dose at various visits during the study as described in [Appendix 1](#).

The date and time of last cerdulatinib dose prior to any PK assessment should be recorded.

Unscheduled plasma samples may also be collected at the discretion of the Investigator (e.g., in the event of an AE) as described in Section [7.3.2.3](#).

### **9.2. Pharmacodynamic Assays**

Serum will be obtained at various time points throughout the trial (detailed in [Appendix 1](#)) to determine the effects of cerdulatinib on markers of inflammation. DNA and RNA will be isolated from optional tumor biopsy specimens to assess genetic mutations relevant to the disease and the mechanism of action of cerdulatinib (see [Appendix 1](#) and the Study Laboratory Manual).

- Quantification of serum proteins.
- Quantitative PCR for tumor relevant transcripts.
- Hybridization of RNA to gene arrays.
- DNA sequencing to identify disease-relevant mutations.

## 10.0 ASSESSMENT OF SAFETY

Safety and tolerability will be monitored and determined by serial physical exams, vital signs, hematology and chemistry laboratory studies, and reported AEs (including deaths and other serious adverse events [SAEs] and treatment-emergent AEs).

### 10.1. Safety Parameters and Definitions

Safety assessments will consist of monitoring and recording adverse events, including serious adverse events and pregnancies; performing protocol-specified safety laboratory assessments; measuring protocol-specified vital signs; and conducting other protocol-specified tests that are deemed critical to the safety evaluation of the study.

Certain types of events require immediate reporting to the Syneos Safety Department, as outlined in Section 10.2.1.

#### 10.1.1. Adverse Events

According to the ICH guideline for Good Clinical Practice, an adverse event (AE) is any untoward medical occurrence in a patient administered a pharmaceutical product, which may or may not have a causal relationship with the treatment. An AE can be any of the following:

- Unfavorable and unintended sign (e.g., including an abnormal laboratory finding), symptom, or disease temporally associated with the use of the study drug, whether or not it is considered to be study drug-related
- Any newly occurring event or exacerbation of previous condition (e.g., increase in severity or frequency) since the administration of study drug
- Recurrence of an intermittent medical condition (e.g., headache) not present at baseline
- Any deterioration in a laboratory value or other clinical test (e.g., ECG, X-ray) that is associated with symptoms or leads to a change in study treatment or concomitant treatment or discontinuation from study drug.
- AEs that are related to a protocol-mandated intervention, including those that occur prior to assignment of study treatment (e.g., screening invasive procedures such as biopsies).

#### 10.1.2. Serious Adverse Event (SAE)

An SAE is any AE, occurring at any dose of any study medication, regardless of causality that:

- Is fatal (i.e., the adverse event actually causes or leads to death).
- Is life-threatening (i.e., in the opinion of the Investigator or Study Sponsor, the patient was at immediate risk of death from the reaction as it occurred).
- Requires inpatient hospitalization or prolongation of existing hospitalization.

- Results in persistent or significant disability/incapacity. Disability is defined as a substantial disruption of a person's ability to conduct normal life functions.
- Is a congenital anomaly/birth defect in a neonate/infant born to a mother who was exposed to study drug or where the father was exposed to study drug before conception. Is an important medical event in the investigator's judgment (i.e., may jeopardize the patient or may require medical/surgical intervention to prevent one of the outcomes listed above). Examples of such medical events include allergic bronchospasm requiring intensive treatment in an emergency room or at home, blood dyscrasias or convulsions that do not result in inpatient hospitalization, or the development of drug dependency or drug abuse.

Clarification should be made between the terms "serious" and "severe," since these terms are NOT synonymous. The term "severe" is often used to describe the intensity (severity) of a specific event (according to NCI CTCAE criteria per section 10.2.2); the event itself, however, may be of relatively minor medical significance. This is NOT the same as "serious," which is based on the strict regulatory definitions listed above and serves as a guide for defining regulatory reporting obligations. A severe adverse event does not necessarily need to be considered serious. For example, persistent nausea of several hours duration may be considered severe nausea but not an SAE if the event does not meet the serious criteria. On the other hand, a stroke resulting in only a minor degree of disability may be considered mild, but would be defined as an SAE based on the above noted serious criteria. Thus, severity and seriousness need to be independently assessed for each AE recorded on the eCRF.

### **10.1.3. Suspected Unexpected Serious Adverse Reactions (SUSARs)**

SUSARs are serious AEs that are both unexpected (i.e., the nature or severity is not expected from the information provided in the IB) and assessed by the Investigator or Portola Medical Monitor to have a reasonable possibility of a causal relationship to the investigational medical product(s). SUSARs require reporting to the Competent Authorities, and Ethics Committees within an expedited timeline (7 calendar days for fatal / life-threatening SUSARs, 15 calendar days for all other SUSARs). Thus it is required that the Investigator complete the SAE form and report all SAEs within 24 hours of his/her awareness of the event to the Syneos Safety Department. Additionally, Syneos Safety Department, on behalf of Portola, will immediately notify the Investigator if any additional safety or toxicology information that impacts patient safety becomes available during the study. All SUSARs will be provided to all Investigators for submission to their respective IRBs per local requirements and when information that impacts patient safety becomes available during the study. It is the responsibility of the Investigator to promptly notify the IRB/Independent Ethics Committee (IEC) of all SUSARs involving risk to human patients.

## 10.2. Methods and Timing for Capturing and Assessing Safety Parameters

The investigator is responsible for ensuring that all AEs (Section 10.1.1 for definition) are recorded on the Adverse Event eCRF and reported to the Sponsor in accordance with instructions provided in this section.

For each AE recorded on the Adverse Event eCRF, the investigator will make an assessment of seriousness (Section 10.1.2), severity (Section 10.2.2), and causality (Section 10.2.3).

### 10.2.1. Adverse Event Reporting Period

To comply with regulatory requirements, all SAEs, regardless of causality, that occur from the date of signing of informed consent until 30 days after the last study drug treatment (or initiation of the next therapeutic regimen prior to the 30 days), must be reported to Syneos Safety Department within 24 hours from Investigator awareness of the SAE.

**After informed consent** has been obtained **but prior to initiation of study drug**, only SAEs caused by a protocol-mandated intervention (e.g., invasive procedures such as biopsies, discontinuation of medications) should be reported to Syneos Safety Department. These pre-dose adverse events will be collected on the AE eCRF and assessed as not related to study drug, but will be assessed for relationship to study procedures/tests and interventions.

**After initiation of study drug**, all treatment emergent adverse events (TEAE), regardless of relationship to study drug, will be reported until **30 days after the last dose of study drug**. Any SAE that occurs with an onset date later than 30 days after completion of the study and that the Investigator considers to be related to study medication must be reported to the Syneos Safety Department.

To report any SAEs, the SAE Report Form provided to the clinical study site must be completed with the available information. The information collected must include at minimum the following: patient number, study drug(s) received, the event term, the serious criteria met for the AE, a narrative description of the event, and an assessment by the Investigator of the severity/intensity of the event and relationship to study drug(s). The SAE report should be sent to Syneos Safety Department by email (see contact information below). Follow-up information on the SAE should be sent promptly by the Investigator to Syneos Safety Department when any additional relevant information about the SAE becomes known to the Investigator, or as requested by Syneos Safety Department.

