**3.1.3. End of Study**

The end of study will occur when all patients have completed the follow-up visit at 30 days post-treatment, or until all patients have died, have been discontinued (under advice of the physician, at the request of the Sponsor), have withdrawn consent, or are lost to follow-up, whichever occurs first.

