#### 4.4. **Withdrawal Criteria and Replacement of Patients**

Patients are free to withdraw from the study at any time for any reason; however, to the extent possible, all patients should continue to participate in the study once they have enrolled, even if they discontinue study drug. The Investigator also has the right to withdraw a patient from the study in case of events such as inter-current illness, AEs, progression, protocol violation, other procedures needed for treatment of their disease, or other medical conditions, administrative reasons or for other reasons (detailed in Section 4.4.1).

An excessive rate of withdrawals can render the study un-interpretable; therefore, unnecessary withdrawal of patients should be avoided. Should a patient decide to withdraw, all efforts will be made to complete and report the observations as thoroughly as possible. Reasons for all discontinuation of study drug and withdrawals from the study will be recorded. If a patient discontinues the study drug due to an AE, that AE must be evaluated to determine if it is a serious adverse event (SAE; see Section 10.1.2). The Investigator must report all SAEs to the Syneos Safety Department (the Sponsor's Safety Designee) on the SAE form within 24 hours from the point in time when the Investigator becomes aware of the SAE. The procedures described under 30 Days Post-Last Treatment (Section 7.3.2.2) will be performed upon discontinuation/withdrawal, whenever possible. If a patient withdraws consent, no further information will be collected after the study termination visit.

Normal study termination is defined as the 30 Days Post-Last Treatment visit in Section 7.3.2.2.

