#### **10.2.4.7. Deaths**

Death should be considered an outcome and not a distinct event. All deaths (including deaths due to progression of the underlying malignancy) that occur during the protocol-defined adverse event period should be reported as SAEs, regardless of attribution to study drug. The event or condition that caused or contributed to the fatal outcome should be recorded as the single medical concept (e.g., respiratory failure) with a fatal outcome. When the event that led to death cannot be identified (e.g., sudden death of unknown origin) report "sudden death" as the adverse event and update it when new information clarifies the event that led to death. Only one AE can be reported with a fatal outcome for each patient who dies. Other AEs that continued up to time of death should be reported with an outcome of not recovered/resolved. In the event that the death is attributed solely to progression of the underlying malignancy, the AE term should be reported as "Disease Progression."

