7.8.1. Adverse Events

Summary tables and listings will be provided for all reported treatment emergent adverse events (TEAEs), defined as AEs that start on or after the first day of any study drug that is administered and within 30 days of the last administration of any study drug. Missing and partially missing AE start dates will be imputed according to the specification described in Appendix A. The reported AE will be coded using MedDRA (version 16.1 for Phase 1; version 21.1 or higher for Phase 2a). AEs severity grading scales in Phase 1 are based on the NCI CTCAE version 4.03. For AEs in Phase 2a, AE severity grades are mixture of grading scales of the NCI-CTCAE version 4.03 and the NCI CTCAE version 5. No imputation of AE grades will be performed. AE with missing CTCAE grade will only be summarized in the all-grade column.

The causal relationship between the occurrence of an AE and each treatment will be assessed by the investigator. For summary of related AEs, causality assessment by the investigator per eCRF will be mapped based on Table 2. If the assessment of the relationship of an AE to study treatment is missing, the AE is assumed to be related to the study treatment in the table summary. No imputation will be done in the AE listings.

Table 2. Causality Mapping of AEs

Relationship to Study Drug per Investigator	Summary of AEs
Unrelated	Not related
Unlikely	Not related
Possible	Related
Probable	Related

TEAEs will be summarized based on the number and percentage of subjects experiencing AEs. When summarizing TEAEs by MedDRA system organ class (SOC) and preferred term (PT), a subject reporting the same AE more than once will be counted only once when calculating the incidence 1) within a given SOC, and 2) within a given SOC-PT combination. Similarly, a same AE will be counted only once within a PT when summarizing by PT only. In both situations, the maximum CTCAE toxicity grade and the strongest causal relationship to the study drug for such events will be used.

Tabular summaries of the following will be provided:

- TEAEs by PT
- TEAEs by SOC, PT
- TEAEs by SOC, PT, and maximum severity grade
- Grade 3 or higher TEAEs by PT
- Grade 3 or higher TEAEs by SOC, PT
- Grade 3 or higher TEAEs by SOC, PT and maximum severity grade
- Cerdulatinib-related TEAEs by PT
- Cerdulatinib-related TEAEs by SOC, PT
- Cerdulatinib-related TEAEs by SOC, PT, and maximum severity grade
- Rituximab-related TEAEs by PT (Cohort 2 only)

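### Protocol 10.2.1 sets SAE reporting windows that cannot all be followed, and leaves related SAEs from day 31 to about day 60 outside its own rules

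*Protocol*

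**What the plan says.** Protocol 10.2.1 (Adverse Event Reporting Period) contains four statements about timing.

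- **Expedited SAEs.** The first paragraph requires reporting of "all SAEs, regardless of causality, that occur from the date of signing of informed consent until 30 days after the last study drug treatment". A bracket can end that window sooner: "or initiation of the next therapeutic regimen prior to the 30 days), must be reported to Syneos Safety Department within 24 hours".
- **Before dosing.** The second paragraph narrows pre-dose reporting to SAEs that arise from something the protocol itself requires, such as a biopsy.
- **After first dose.** The third paragraph has all TEAEs, related or not, reported up to 30 days after the last dose. It says nothing about new therapy.
- **Late events.** The same paragraph then makes drug-related events of this kind reportable: "Any SAE that occurs with an onset date later than 30 days after completion of the study and that the Investigator considers to be related".

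Two other sections bear on what completing the study means. Section 4.4: "Normal study termination is defined as the 30 Days Post-Last Treatment visit". Section 3.1.3, for the trial as a whole: "The end of study will occur when all patients have completed the follow-up visit at 30 days post-treatment".

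Section 10.2.4.7 ties death reporting to the same period: deaths "that occur during the protocol-defined adverse event period should be reported as SAEs, regardless of attribution to study drug". SAP 7.8.1 (Adverse Events) counts events that start from first dose and "within 30 days of the last administration of any study drug", again with no stop at new therapy. It tabulates serious and fatal TEAEs, and splits deaths into those within and those beyond 30 days of the last dose.

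**The concern.** The late rule changes its reference point. Routine reporting is counted from the last dose, but late reporting is counted from completion of the study, which for a patient comes about 30 days afterwards. Between the end of one rule and the start of the other lies a stretch in which 10.2.1 asks for nothing, even for an event the investigator attributes to the drug.

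The next-regimen bracket raises a different problem. It appears in one sentence and not in the TEAE sentence or the SAP, so a site can follow either and believe it complies. Leaving treatment for other therapy is foreseen: progression requiring other therapy is the first withdrawal criterion in 4.4.1.

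The stake is mainly safety reporting. Section 1.5 reports fatal lung infection and fatal *Pneumocystis* pneumonia, both considered related, in Phase 1. Section 3.1.2.2.1 reports two fatal infections among the first 12 Phase 2a patients reviewed. Section 11.5 states that there is no formal DSMB. In that setting the reporting period should be free of doubt.

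**Working it through.** The plan gives no figure here to reproduce. The check is a side-by-side reading with day counts, taking the date of last dose as day 0.

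**1. Late related SAEs.** Inputs: routine window closes on day 30 (10.2.1); patient-level termination is the 30-day visit (4.4); that visit may fall on day V = 30 ± 3 (Appendix 1). The late rule opens after day V + 30. Uncovered onset days run from 31 to V + 30, a count of (V + 30) − 30 = V.

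- V = 27: late rule opens after day 57; days 31 to 57 uncovered, 27 days.
- V = 30: opens after day 60; days 31 to 60 uncovered, 30 days.
- V = 33: opens after day 63; days 31 to 63 uncovered, 33 days.

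If the late rule is counted from the last dose, it opens after day 30 and the gap is 0 days.

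**2. End of the window.** If the next regimen starts on day N, before day 30, then 30 − N days lie inside the TEAE sentence and the SAP window but outside the expedited SAE sentence. The documents give no distribution for N, so these values are assumed:

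- N = 7: 30 − 7 = 23 days.
- N = 14: 30 − 14 = 16 days.
- N = 21: 30 − 21 = 9 days.

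**3. Deaths.** Suppose new therapy starts on day 14 and the patient dies on day 20. If the TEAE sentence defines the adverse event period, 10.2.4.7 makes the death an SAE. If the expedited sentence defines it, the period closed on day 14. The protocol does not say which applies. The SAP counts the death as within 30 days either way.

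**4. Before dosing.** Take a consented, undosed patient who is hospitalised for a reason unconnected with any study procedure. Paragraph one says report. Paragraph two says only procedure-caused SAEs are reported. Both cannot be followed.

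**The case against.** The strongest reply is that other text still brings these events in.

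- The TEAE sentence covers serious events to day 30. Section 10.2 requires all AEs on the eCRF, each assessed for seriousness. Section 7.3.2.2 and Appendix 1 keep the 30-day visit, with AE assessment, and make no exception for new therapy. This stands. A reader might infer that SAE collection simply ends at the next regimen, or that the SAP's serious and fatal TEAE rates are biased, more so in some cohorts. The documents support neither inference: they show conflicting instructions, and they contain nothing on differences between cohorts.
- Section 10.1.3 asks for all SAEs within 24 hours of awareness, and 4.4 says much the same in the context of discontinuation. Neither names a window. This stands in part. It means that 10.2.1 is not the only route for a late event, so one should not say that late related SAEs can never be reported. But those sentences govern speed, while 10.2.1 is the section that defines the period, so they add a further statement to reconcile.
- The removal of long-term follow-up in Amendment 9 might be read as having closed the last route for late events. The amendment summary lists the AE assessment at that visit as an error in Amendment 8, so it does not show that AEs were meant to be collected there.
- *Completion of the study* may have been meant as completion of study treatment. That would close the gap, but no section defines it so.

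**Conclusion.** The point holds as a contradiction within Protocol 10.2.1, and between its expedited SAE sentence and SAP 7.8.1. Related SAEs starting from day 31 to about day 60 (27 to 33 days, given the visit window) fall under neither of its post-dose rules. The expedited sentence and the TEAE sentence end on different days for anyone who starts new therapy before day 30. The two pre-dose rules conflict outright.

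The first figure assumes that completion means the patient's 30-day visit, as 4.4 suggests. A reader might take it as the trial-level end of study in 3.1.3 and arrive at a gap of years. That equates two different terms, and the documents do not make the link.

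A reader might also calculate that someone starting new therapy on day 10 loses two thirds of the SAE window (20 of 30 days). The SAP has no 30-day denominator: it reports the number and percentage of subjects with an event, over a window that opens at first dose. With an assumed two 28-day cycles the affected share is 20/(56 + 30) = 20/86, about 23%. Even that is time under conflicting instructions, not lost data.

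The gap after day 30 leaves the TEAE tables unchanged, because they stop at day 30; it matters for safety reporting. Any effect on analysis comes through the next-regimen clause, as a risk of inconsistent capture or reconciliation of serious and fatal TEAEs. This should be corrected, though it does not undermine the safety analysis.

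**What to change.** Rewrite 10.2.1 around one reference point.

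- **Late rule:** an SAE starting more than 30 days after the last dose of study drug, and judged related by the investigator, is reportable. Remove the reference to study completion.
- **End of window:** delete the next-regimen clause, so that AEs, SAEs and deaths all run to 30 days after the last dose of any study drug, as in the SAP. Adding the same clause to the TEAE sentence and the SAP would also remove the contradiction, but would shorten the analysis window.
- **Before dosing:** start paragraph one at first dose, so that paragraph two alone governs pre-dose SAEs.
- **SAP:** keep the 30-day window and flag, in the serious and fatal TEAE listings, events that start after new therapy.

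The cost is protocol wording, a memo to sites and one flag in the AE programs. The downside is a few additional SAE reports that may be due to the next therapy; the flag lets a reader identify them.
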